For the evaluation of implementation components, we conducted similar sensitivity power analyses in order to calculate the minimum detectable Cohen's D effect size to obtain a significant effect of each component level on implementation outcomes of participation rates and implementation quality. Following recommendations for component selection by Collins et al. (2016) and Watkins et al. (2016), we assumed a Type 1 error of $p < 0.10$, and 80% power with a sample size of 480 adults and an ICC of

0.05. Thus, this sample size has sufficient power to detect significant component effects at Cohen's $d = .26$ on implementation outcomes (i.e., implementation fidelity, competent adherence, and participation).

14. Interventions

Intervention group – Parenting for Respectability

PfR was developed over five years following the Six Steps for Quality Intervention Development (6SQuID) model [22]. It initially underwent formative evaluation over two years (2014-2016) with six groups in three villages in Wakiso District [20]. *PfR* is a 16-session manualised programme starting with nine single sex sessions followed by seven mixed sex sessions, delivered once a week by two local facilitators who receive one week's training [23]. The programme draws on parents' pre-existing motivation to maintain respectability, largely achieved through children's good behaviour and respect for elders and builds on parents' existing skills and experience. Activities were developed specifically for PfR or adapted from other parenting programs, including *Project H*, *Stepping Stones*, *Mema kwa Jamii*, the *International Child Development Programme* and *Parenting for Lifelong Health* [24]. The programme addresses four familial processes associated with GBV and VAC: poor parental bonding and child attachment; harsh parenting; inequitable socialisation by gender and parental conflict. A particular goal is to involve fathers, whom most parenting programmes find hard to recruit, and the first nine sessions are delivered in single-sex groups. The intervention's rationale, program theory and formative evaluation are described elsewhere [25].

Control group - Lecture

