Data collected from the process evaluation will investigate the implementation of the PfR programme. Quantitative data will be collected to examine implementation fidelity, competent adherence, and participation. Qualitative data will also examine barriers to implementation and participation, and potential approaches to overcoming these barriers.

Recruitment rate – Assessor Report

Recruitment rate will be based on the number of families who were eligible for inclusion and provided consent to participate in the program divided by the number of target population who were exposed to recruitment activities.

[Time Frame: 8-months post-baseline]

Enrolment rate – Facilitator Report

Enrolment rate will be based on the number of families who attend either at least one session of *Parenting for Respectability* or the *Parenting in a Nutshell* lecture divided by the number of families allocated to either study arm. Separate enrolment rates will be assessed for each arm

[Time Frame: 8-months post-baseline]

Participation rate – Parenting for Respectability participants only – Facilitator Report

Participation rates for those allocated to the PfR programme will be mean attendance rate for programme sessions based on those families who enrolled in the programme (i.e., parents who attended at least one session). We will also assess the percentage of families who enrolled in the programme who attended 50% (e.g., 8 sessions) and 75% (e.g., 12 sessions) or more.

[Time Frame: 8-months post-baseline]

Dropout rate – Facilitator Report

Dropout rates for enrolled participants will be defined as the percentage of participants who fail to attend at least three consecutive sessions and do not attend any sessions at a later stage.

[Time Frame: 8-months post-baseline]

Completion rate – Facilitator Report

Completion rates for participants will be determined based on the number of enrolled participants who attend a cut-off threshold of at least 62.5% of the programme (i.e., 10 sessions) [38].

[Time Frame: 8-months post-baseline]

Implementation dosage (time) – Facilitator Report

Implementation dosage will be based on the total amount of time in minutes that the program was delivered to each parent. Facilitators will report on the start and end time of each session/lecture in their weekly reports. Implementation dosage will be based on the total amount of time delivered divided by the mean attendance rate.

[Time Frame: 8-months post-baseline]

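### The formula for implementation dosage divides by the attendance rate and so cannot give the minutes per parent that the same paragraph defines as the outcome

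*Protocol*

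**What the plan says.** The protocol's section 15, Process outcomes, has a short paragraph on implementation dosage (time). Its first sentence names the quantity: "Implementation dosage will be based on the total amount of time in minutes that the program was delivered to each parent". The second gives the data source: "Facilitators will report on the start and end time of each session/lecture in their weekly reports". The last gives the calculation: "Implementation dosage will be based on the total amount of time delivered divided by the mean attendance rate".

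The attendance rate is described a little earlier under the same heading. Participation for the PfR arm "will be mean attendance rate for programme sessions based on those families who enrolled in the programme". It is expressed as a share of sessions, with cut-offs for families who "attended 50% (e.g., 8 sessions) and 75% (e.g., 12 sessions) or more". The completion threshold is in the same terms: "at least 62.5% of the programme (i.e., 10 sessions"). Section 14 gives the number of sessions: PfR "is a 16-session manualised programme starting with nine single sex sessions followed by seven mixed sex sessions".

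The dosage formula is not restated or corrected anywhere else in the protocol.

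**The concern.** The first and last sentences of the paragraph describe different quantities. Minutes delivered to a parent cannot exceed the minutes run, and should fall when that parent attends less. Dividing time run by a proportion does the opposite on both counts.

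This is not a detail left to the statistical analysis plan. The protocol states the rule, and section 26 commits the study to analysing data as the registered protocol says. An analyst who follows the sentence literally would report a dose that no parent could have received. If attendance rates were taken separately by group, the least exposed groups could appear the most exposed.

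**Working it through.** **Inputs.** Number of sessions: 16 (section 14). Attendance rate a: a proportion of sessions, with 50% equal to 8 sessions, 62.5% to 10 and 75% to 12 (section 15). Session length L: not given in the protocol, so 120 minutes is assumed for illustration and 60 to 180 is shown as a range. Clock time run is T = 16 × L. The protocol states no dosage figure, so there is nothing to reproduce.

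**Step 1: clock time as numerator.** Facilitators record start and end times per session, so the natural numerator is T. The written formula is T / a. Mean minutes received per enrolled parent is T × a when sessions are of equal length. The ratio of the two is (T / a) / (T × a) = 1/a². With L = 120, T = 16 × 120 = 1,920:

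| a | As written, T / a | Received, T × a | Ratio 1/a² |
|---|---|---|---|
| 1.00 | 1,920 | 1,920 | 1.00 |
| 0.75 | 2,560 | 1,440 | 1.78 |
| 0.625 | 3,072 | 1,200 | 2.56 |
| 0.50 | 3,840 | 960 | 4.00 |
| 0.25 | 7,680 | 480 | 16.00 |

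Every value in the second column below full attendance is larger than the 1,920 minutes that were run.

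**Step 2: session length.** At a = 0.50 the written formula and the minutes received are 1,920 and 480 (L = 60), 2,880 and 720 (L = 90), 3,840 and 960 (L = 120), and 5,760 and 1,440 (L = 180). The ratio is 4 each time; L cancels.

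**Step 3: which attendance rate, and which numerator.** Take two groups of equal size, both with T = 1,920, one at 75% and one at 50% attendance. Minutes received are 1,440 and 960. The overall mean rate is 62.5%.

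- Clock time divided by each group's own rate: 2,560 and 3,840. The order is reversed.
- Clock time divided by the overall mean: 1,920 / 0.625 = 3,072 for both. The level is inflated and the order of the numerators is kept (here a tie), but the difference in attendance is lost.
- Minutes received divided by the overall mean: 1,440 / 0.625 = 2,304 and 960 / 0.625 = 1,536. Levels are inflated by 1/0.625 = 1.6; the order is correct.
- Minutes received divided by each group's own rate: 1,440 / 0.75 = 960 / 0.50 = 1,920. Attendance cancels.

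Reversal in the first case also needs similar delivered time. Write r for the time run in the better-attended group divided by that in the other. The written formula puts the better-attended group lower when r < 0.75 / 0.50 = 1.5, and minutes received put it higher when r > 0.50 / 0.75 = 0.67. The order is therefore reversed for r between 0.67 and 1.5.

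**Step 4: other meanings of the divisor.** If the rate meant mean sessions attended, T / (16a) goes from 120 to 240 as a falls from 1 to 0.5. If it meant mean attendees in a group of 10, T / (10a) goes from 192 to 384. Both still rise as attendance falls.

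None of the readings tried gives minutes per parent once attendance is incomplete.

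**The case against.** The strongest defence concerns consequence. Dosage is one process measure, and its first sentence already names the right target. Session times and attendance are recorded separately, so the correct variable can be derived later without loss. No stated result or sample size depends on the formula. All of this stands.

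A reader might infer that the error undermines objectives 3 and 4. The protocol does not support that. Objective 3 concerns participation, fidelity and delivery quality; objective 4 concerns engagement and delivery quality. The component analyses in section 20 list participation, fidelity, quality and cost. Overall exposure is assessed there from attendance registers, and the complier analysis names fidelity and attendance. None names dosage. The nearest link is the exploratory regression of feasibility outcomes on change scores under Implementation outcome analyses, where dosage could enter but is not named.

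A reader might also infer that every dose comparison is reversed. That requires group- or parent-specific rates together with similar delivered time. The text speaks of a single mean attendance rate, and on that reading order is not reversed. Likewise the 1/a² factor requires clock time as numerator. With minutes received over one overall mean, the inflation is 1/a, which is 2-fold at 50% rather than 4-fold.

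What the defence does not do is make the sentence right.

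**Conclusion.** The point holds as an internal contradiction in the definition of one process outcome. The definition asks for minutes per parent, and the formula does not produce that on any reading examined.

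On the most natural reading, with session clock time as numerator, it overstates mean minutes received by 1/a²: about 1.8-fold at 75% attendance, 2.6-fold at the 62.5% completion threshold and 4-fold at 50%. That factor does not depend on session length, but it does assume sessions of equal length, or attendance unrelated to length. The minute figures rest on the assumed 120 minutes. Reversed ranking is a conditional risk, not a certainty.

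No primary, secondary or cost-effectiveness outcome is defined through dosage, so the trial's main conclusions are not at stake. The correction is still worth making before analysis, because the rule is stated explicitly and could carry into the exploratory regressions.

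**What to change.** Replace the last sentence of the dosage paragraph with: *Implementation dosage per parent is the sum of the recorded minutes of the sessions that parent attended (facilitator start and end times linked to the attendance register), summarised as the mean across enrolled parents.*

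Multiplying total minutes by the attendance proportion should be treated only as an approximation, because it ignores which sessions were missed. For example, with two sessions of 60 and 180 minutes (assumed), a parent who attends only the longer one receives 180 minutes, whereas 240 × 0.5 gives 120.

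The cost is one sentence of protocol wording. Session times (section 15) and attendance registers (section 18) are already to be collected, so no new data and no change of design are needed.

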C) Facilitator Experience (professional vs community). We hypothesise that although professional facilitators may achieve higher levels of implementation, community facilitators may be a more cost-effective approach and may also result in better implementation due to stronger buy-in at the community level. As a result, there will be no difference between components on VAWC (via indirect effects).

8. Trial design

We will use an effectiveness-implementation hybrid type 2 design to a) determine the effectiveness and cost-effectiveness of PfR, and b) determine the feasibility and impact of three different implementation strategies in terms of programme delivery.[21] We will conduct a cluster randomised controlled trial (cRCT) in a total of 54 clusters (1:1 intervention: control; 4 groups of 10 parents per cluster, 50% male 50% female, 2,160 in total or 1,080 adult participants per arm). In addition, approximately 1,080 children 10-14 years will be assessed ($N = 540$ per arm). We will also assess the quality of delivery of PfR in terms of competent adherence of 108 facilitators (1 per group, 4 per cluster).

We will also examine three different factors related to programme implementation within the clusters allocated to PfR (approximately 27 clusters, 40 parents per cluster): 1) geographical location (rural vs. peri-urban), 2) group composition (existing vs. newly formed groups), and 3) facilitator experience (experience vs. novice). Efforts will be made to have equal numbers of clusters receiving each type of component by testing every combination of implementation components in eight different experimental conditions ($N 3$ clusters and 120 families per condition).

Section 3: Methods

9. Study setting

The study will be conducted in two districts, Wakiso and Amuru, each of them contributing parental participants to both intervention and control arms. Participating clusters will either be villages or wards (i.e., groups of villages) depending on their population size and geographical proximity.

10. Eligibility criteria

Participants must have provided written, informed consent prior to the occurrence of any study procedures.

Inclusion criteria for participating parents or caregivers:

1. Age 18 or older;
2. Primary caregiver responsible for the care of a child between the ages of 10 and 14;
3. Agreement to participate in the PfR programme if allocated to the treatment condition;
4. Provision of consent to participate in the full study.

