Time cost for delivery – Facilitator Report

Time cost for delivery will be collected from facilitator weekly reports and based on the time spent on training, preparation, travel to and from, and delivery of each session/lecture. The total time will be summed for each facilitator and then mean scores will be created for the sample.

[Time Frame: 8-months post-baseline]

Implementation fidelity – Facilitator Report

Implementation fidelity by programme facilitators of the PfR programme will be examined using self-report checklists by the programme facilitators. They will report on 5 items per session/lecture ranging from an impression of the quality of delivery to the proportion of the session activities they were able to deliver (0 = No time for it to 5 = all of the activities).

[Time Frame: 8-months post-baseline]

Competent adherence – Observational

Competent adherence will be assessed using the PfR Facilitator Assessment Tool (PfR-FAT) [39]. The PfR-FAT was developed by the study investigators and programme developers to assess the proficiency of programme delivery by facilitators as a prerequisite to certification. Three standard behaviour categories are based on the core process skills (25 items), includes modelling skills (6 items, e.g., “give positive, specific, and realistic instructions”), collaborative facilitation (7 items, e.g., “accept participant responses verbally by reflecting back what the participant says”), and group management and leadership

skills (12 items, e.g., “use open-ended questions during group discussions”). Items are summed to create a total score of competent adherence.

[Time Frame: 8-months post-baseline]

Qualitative outcomes

Qualitative data will be collected using live observation of programme delivery (at least 1 observation per group, N=32); in-depth interviews with senior implementation staff (N=4), trainers of facilitators (N=2) and a sample of facilitators (N=16); focus group discussions with caregivers (N=8, 10 per FGD). In addition, data will be collected through semi-structured interviews with Wakiso and A District Community Development Services (N=4) who will provide supervision of the NGO implementing partner (SOS) and from a sample of local community leaders (N=8), each lasting from 60 – 90 minutes.

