Interviews and focus groups will occur during the post-evaluation and examine the following themes: 1) participants observed change in parenting practices and child behaviour at home during programme; 2) acceptability and appropriateness of programme materials, delivery, and key programme components; and 3) existing barriers to participation during sessions and engagement in home practice and other activities. Interviews will also explore facilitators’ challenges in implementing the programme on both a process (e.g., using a collaborative approach and/or explaining concepts such as child-led play) and logistical level (e.g., recruitment, session length, location, meals).

Cost effectiveness data collection

Programme costs will be calculated using a micro-costing approach, multiplying resource use by unit costs, divided into 1) start-up costs including costs required for coordinating recruitment, community mobilisation, and facilitator training; 2) programme delivery costs which includes staff-time, transportation, and other materials for home-based individual consultations, parent-group sessions, and supervision sessions; and 3) administrative costs to manage the implementation.

17. Blinding

The allocation status of other participating families will be concealed from participants, thus reducing the potential for contamination. Research assistants conducting data assessments and statisticians conducting analysis will be blind to allocation in order to minimise assessment bias [40, 41]. Different groups of research assistants will be employed for outcome assessments and monitoring of implementation fidelity and adherence. Any instances of compromised blinding will be immediately reported. In the case of instances of harm or severe abuse being reported by a participant at any stage of the study, the allocation status of the participant will be un-blinded. All cases of un-blinding will be reported. Because of facilitators’ involvement in the programme implementation, blinding will not be possible for service providers. Similarly, of course, participants cannot be blind to their own treatment condition.

18. Data collection, retention, and management

Data collection

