Data collectors who are fluent in Luganda for Wakiso and Acholi for Amuru and who have prior experience working with vulnerable families in Uganda will serve as research assistants. They will be extensively trained in ethics, informed consent, interviewing, and observational assessment techniques by the study investigators. All data collection points will have a detailed protocol and will be scripted to ensure consistency across data collectors. Research assistants will be managed by the project coordinator ([name]) and supervised by PI [name]. Quantitative self-report assessments and qualitative interview/focus group guides will be translated into Luganda and Acholi by bilingual researchers and the translation checked by back-translation [42].

The proposed study will use an innovative, low-cost technological data collection tool using Computer-Assisted Self-Interviewing ('CASI') methods with e-tablet technology to administer consent forms and questionnaires. This method of data collection has been pilot-tested during the previous feasibility study with high acceptability to respondents. Trained data collectors will explain the CASI procedures, read out questions, and assist participants to key in responses to their handsets. CASI supports multiple languages, and so can include English, Luganda, and Acholi. If any participants are unable or uncomfortable with the use of tablets, a paper-and-pen interviewer-assisted questionnaire will also be available in English, Luganda, and Acholi.

Data on implementation fidelity will be collected live at all programme sessions. Programme adherence data will be collected using attendance registers administered by research assistants assigned to the process evaluation. Programme participants will indicate whether they completed their home activity assignments using self-report checklists.

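### Section 15 takes attendance from the facilitators being compared, while Sections 18 and 20 use research-assistant registers; separately, 32 qualitative observations cannot cover 108 groups

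*Protocol*

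**What the plan says.** **Attendance.** Under Process outcomes, Section 15 labels enrolment, participation, dropout and completion as facilitator-reported. Section 18 (Data collection) says "Programme adherence data will be collected using attendance registers administered by research assistants assigned to the process evaluation". Section 20 (quantitative analysis of programme implementation) bases exposure, adherence and engagement on attendance registers.

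**Fidelity.** Section 15 says "Implementation fidelity by programme facilitators of the PfR programme will be examined using self-report checklists by the programme facilitators". The checklist has five items per session, and they include the facilitator's own impression of how well the session was delivered. Section 17 says "Different groups of research assistants will be employed for outcome assessments and monitoring of implementation fidelity and adherence", and Section 18 says "Data on implementation fidelity will be collected live at all programme sessions". Section 20 analyses both the checklists and the observational PfR Facilitator Assessment Tool (PfR-FAT), and compares the two methods on overall fidelity scores.

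**Competent adherence.** Section 15 labels it observational, scored with the PfR-FAT. Section 8 sets its coverage: "competent adherence of 108 facilitators (1 per group, 4 per cluster").

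**What is compared.** Objective 3 (Section 7) and the implementation component analyses in Section 20 compare facilitator types on participation, fidelity and quality of delivery. Section 20 adds cost.

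**Qualitative observation.** The qualitative outcomes in Section 15 list "live observation of programme delivery (at least 1 observation per group, N=32").

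**The concern.** A data manager reading Section 15 would build the attendance outcomes from facilitator reports. One reading Sections 18 and 20 would build them from registers kept by research assistants. The choice matters because one of the three implementation factors is the type of facilitator. Under Section 15 the people being compared supply the participation data and grade their own fidelity. If professional and community facilitators differ in how fully they record attendance, or in how generously they rate themselves, that difference cannot be told apart from a real difference in delivery. The implementation comparison is already nonrandomised (Section 7), so it has little room for a further, avoidable source of bias.

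Attendance and fidelity also enter the complier average causal effect analysis and the exploratory regressions on change in the primary outcomes (Section 20). The choice of source therefore reaches beyond Objective 3.

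The qualitative observation item is a separate problem: its stated coverage and its stated number cannot both be true.

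**Working it through.** **Step 1. Source of each measure, by section**

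| Measure | Section 15 | Elsewhere |
|---|---|---|
| Enrolment, participation, dropout, completion | Facilitator | Registers kept by research assistants (18); exposure and engagement from registers (20) |
| Implementation fidelity | Facilitator checklist | Monitoring by research assistants (17); live at every session, recorder not named (18); checklist and PfR-FAT (20) |
| Competent adherence | Observed, PfR-FAT | 108 facilitators (8) |
| Dosage (session times), time cost | Facilitator | No other source named |

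The first row is a direct conflict. The second leaves the recorder unclear. The third is consistent.

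**Step 2. Which facilitator comparisons are exposed.** Of the outcomes named in Objective 3 and Section 20, participation and fidelity are facilitator-reported under Section 15, and so is the time-cost input to cost. Quality of delivery, measured as competent adherence, is not. The check in Section 20 compares self-report with observation over all facilitators by t-test. It does not ask whether the gap differs by facilitator type, and it does not cover attendance.

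**Step 3. Scale.** The protocol gives no estimate of any reporting difference, so its size cannot be derived. As a yardstick, Section 13 sizes the component comparisons for d = 0.26. A recording difference of D percentage points reaches that size when the standard deviation of attendance is D/0.26. Two assumed values of D:

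- D = 5: 5/0.26 = 19 points
- D = 10: 10/0.26 = 38 points

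At any smaller standard deviation, the reporting difference alone would exceed the effect that the comparison is sized to detect.

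**Step 4. Number of PfR groups.** Section 8 gives "54 clusters (1:1 intervention: control; 4 groups of 10 parents per cluster, 50% male 50% female, 2,160 in total or 1,080 adult participants per arm") and, for the implementation comparison, "approximately 27 clusters, 40 parents per cluster".

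- PfR clusters: 54/2 = 27
- PfR groups: 27 x 4 = 108, which reproduces the 108 in Section 8

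**Step 5. Can 32 be at least one observation per group?**

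| Variant | Groups | 32 as a share |
|---|---|---|
| 27 clusters, 4 groups each | 108 | 30% |
| 24 clusters (after the cluster dropout in Section 13), 4 groups each | 96 | 33% |
| 27 clusters, groups merged in pairs (assumed) | 54 | 59% |
| 24 clusters, groups merged in pairs (assumed) | 48 | 67% |

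No variant gives 32. On the protocol's own count, at least 108 - 32 = 76 groups would go unobserved.

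**The case against.** The strongest reply is that this is mostly a matter of labels. If the registers in Sections 18 and 20 are the working source, facilitators do not report attendance at all. Hypothesis 5 names attendance, competent adherence and cost-effectiveness, and leaves self-rated fidelity out. The delivery-quality measure is observed, and Section 20 already sets self-report against observation. Much of this stands. But Section 15 is where the outcomes are defined, and it says otherwise. Objective 3 and Section 20 include fidelity among the compared outcomes, and the planned check is neither by facilitator type nor about attendance.

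Four stronger readings are tempting, and the protocol does not support them:

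- **Almost every compared outcome is self-reported.** Competent adherence is observed, and attendance has a second, independent source in Section 18.
- **The observed delivery measure covers only 30% of groups.** N=32 is listed with the interviews and focus groups. Nothing ties it to PfR-FAT scoring, which Section 8 sets at 108 facilitators.
- **Live collection at all sessions means 1,728 observations (108 x 16).** Section 18 names no observer, and a checklist completed at each session could satisfy it. The session count would also fall to 27 x (9 x 4 + 7 x 2) = 1,350 if groups merge in pairs for the mixed-sex sessions. For the same reason, the fidelity passages are unclear rather than flatly contradictory.
- **The 32 are four groups in each of eight conditions.** The arithmetic fits (8 x 4 = 32), but the protocol does not say so.

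**Conclusion.** Two inconsistencies hold. First, Section 15 assigns enrolment, participation, dropout and completion to facilitator report, while Sections 18 and 20 point to registers kept by research assistants. Following Section 15 would expose the facilitator-type comparison of participation and fidelity to differential reporting. How large that bias would be cannot be known from the protocol, and the yardstick in the working rests on assumed values. Second, one qualitative observation per group needs at least 108, and 32 is 30% of that. Even the most lenient count, which assumes merged groups and six lost clusters, needs 48.

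The consequence falls on the implementation objectives and the analyses that use attendance or fidelity. The intention-to-treat comparison of PfR with the lecture on the primary outcomes does not depend on these data. The point should be settled before data collection, but it is no threat to the main effectiveness result.

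**What to change.** 1. In Section 15, name the research-assistant register as the source for enrolment, participation, dropout and completion, in line with Sections 18 and 20. Enrolment also counts attendance at the control lecture, so state whether the register covers that too.
2. Base facilitator-type comparisons of delivery quality on the observed PfR-FAT score for all 108 facilitators, as Section 8 already provides. Report the self-report checklist as supportive.
3. Correct the qualitative item in one of two ways. Either remove the promise of one observation per group and state that 32 is a subsample and how it is selected, or correct the number. Neither should reduce PfR-FAT coverage.

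The cost is protocol wording: the registers, the staff who keep them and the observation tool are already planned. If 32 is raised to match the number of groups, that option adds observation visits. Dosage and time cost remain facilitator-reported, and facilitator-type comparisons that use them should be interpreted with that limit.
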